2.3. Research Hypothesis

2.3.1. Hypothesis I.

We expect that the frequency and quality of provider communication about sexuality will increase following provider training.

2.3.2. Hypothesis II.

We expect that the Skills-based patient training program will be feasible and acceptable and that patients will report increased pre- to post-training beliefs and improved sexual function and other health outcomes at 2-month follow-up compared to the Control condition.

2.3.3. Hypothesis III.

We expect that patients receiving the Skills-based training will be more likely to ask a question pertaining to sexuality and raise the topic of sexuality than patients in the Control condition.

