13.3. Outcomes and Statistical Analyses for Patient Training Study (Phase III)

13.3.1. Primary Outcomes

- (1) Patients' **self-efficacy** and **outcome expectancies** for communicating about sexual health with their provider, and
- (2) (A) **The proportion of visits in which the patient asks at least one question pertaining to sexual health**, and (B) **the proportion of clinic visits in which the patient raises the topic of sexual health**, both at post-training clinic visit

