13.3.2. Secondary Outcomes

- (1) Feasibility and acceptability, as measured through recruitment and retention rates, and by acceptable responses on the Program Evaluation
- (2) Sexual function, as measured through the PROMIS SexFS Brief Profile (Female) score
- (3) Sexual activity, as measured through a single item on the PROMIS SexFS Brief Profile (Female)
- (4) Patients' self-efficacy (measured via the PEPPi-5 and 6 additional self-efficacy items) and outcome expectancies for communicating about treatment side effects in general and menopausal health with their provider,
- (5) Patients' self-reports of barriers to communicating about sexual health
- (6) Patient self-reports of psychological health (Hospital Anxiety and Depression scores)
- (7) Patient self-reports of QOL (FACT-B total score)

An exploratory outcome may also be the number of questions a patient asks overall per visit. Additional outcomes are shown in the Patient Training Study Patient Self-Report Measures Table. Data will be obtained on these other measures

to generate hypotheses which can be tested in future studies and will be analyzed according to standard procedures, similar to those described for the main outcomes as below.

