Prior to conducting quantitative analyses, the audio recorded clinic visits will be coded, using a similar strategy as described for the Provider Training Study (Phase II), which centers on the newly developed sexuality dialogue codebook, but can also include other communication behaviors or topics that emerge as important through the coding analyses. To test the hypothesis that patient communication behaviors differ for those in the Skills-based vs. Control conditions, we will use Fisher's exact tests. If a patient asks 1 or more questions during the visit, they will be coded as "yes" for outcome 2A and "no" otherwise. If a patient brings up the topic of sexual health they will be coded as "yes" for outcome 2B. If no one brings up the topic of sexual health, they will be coded as "no". If the provider brings up sexual health, these visits will be excluded from analysis of outcome 2B, as it is impossible to know if the patient may have brought up sexual health if the doctor had not done so. In preliminary data from phase II, these communication behaviors were so rare that Fisher's exact tests will be primarily used. If possible, we will also conduct logistic regression analyses accounting for within-provider correlation using random effects (estimated via generalized linear mixed models, similar to the models described above).

In supplementary analyses, we may examine patient factors that may moderate effects on patient outcomes (e.g., age, partnered status, metastatic disease) by including the moderator, study arm, and study arm by moderator interaction terms in generalized linear mixed models. We may also conduct secondary regression analyses to verify the conclusions of primary models, to assess the sensitivity of inferences to the assumptions of the mixed effects models. For example, we may use Generalized Estimating Equations as confirmatory models, or use logistic or ordinal logistic regressions if the semi-continuous outcome measures cannot be transformed so that the assumptions of the linear regression model are met.

Secondary Analyses

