13.3.4. Sample Size Calculations

The sample size calculations are based on the primary belief outcomes. Based on prior literature,⁹⁰ we assume a standard effect size of .60 on the outcome of patient beliefs. We therefore aim to accrue up to 144 patients (72 per arm) in order to collect an estimated 128 audio recordings (64 per arm) to have 80% power to detect a standard effect of 0.5, with 5% two-sided type-I error.

Other primary outcomes include A) the proportion of visits where the patient asks a question, and B) the proportion of visits where the patient brings up sexual health. Based on preliminary data, we expect these proportions to be low in the control arm (15% and 22%, respectively). We also anticipate that 70% of visits will be informative for outcome B (only visits where the physician does NOT bring up sexual health to be included). Therefore, with sample size of 128 audio recordings, we will have 80% power with 5% 2-sided type-I error to detect rates of 38% for outcome A in the intervention arm versus 15% in the control arm (calculations using Fisher's exact test). For outcome B, assuming 45 informative visits per arm, we will have sufficient power to detect rates of 52% in the intervention arm versus 22% in the control arm.

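### The coding rule for primary outcome 2A (Phase III) omits the restriction to sexual-health questions, and the sample size section leaves unclear which variable its 15% control rate describes

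*Combined protocol and SAP*

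**What the plan says.** Four places in the combined protocol and SAP bear on outcome 2A.

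- **Definition (13.3.1):** "The proportion of visits in which the patient asks at least one question pertaining to sexual health", assessed at the clinic visit after training.
- **Hypothesis III (2.3):** trained patients "will be more likely to ask a question pertaining to sexuality and raise the topic of sexuality" than controls. The study design summary in Section 1.0 carries the same topic restriction.
- **Coding rule (13.3.3):** "If a patient asks 1 or more questions during the visit", the visit is a yes for 2A, and otherwise a no. No topic is named. The sentences on 2B that follow name sexual health each time.
- **Sample size (13.3.4):** outcome A is "the proportion of visits where the patient asks a question", again with no topic, at 15% in the control arm. Outcome B, in the same sentence, keeps its topic.

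Section 13.3.2 lists a different measure as a possible exploratory outcome: "the number of questions a patient asks overall per visit".

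**The concern.** The rule in 13.3.3 is complete: it says what makes a visit a yes and makes every other visit a no. A coder who applies it as written scores a question about scan dates as a success on a primary outcome. That is not the variable in 13.3.1, and a difference between arms on it would not answer Hypothesis III.

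The error could run in either direction. Questions on other topics could hide a real effect on sexual-health questions. Or the training could prompt more questions on other topics and produce a positive 2A result with no change in sexual-health questions. This second route is plausible because the module also covers menopausal health and general communication skills (4.3.3).

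Two written versions of a primary outcome also leave room to choose between them after the recordings are coded.

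**Working it through.** **Step 1: compare the texts.** Sections 13.3.1, 2.3 and 1.0 restrict the topic. Sections 13.3.3 (2A rule) and 13.3.4 (outcome A) do not. The coding rule and the power text therefore agree with each other, and both are looser than the definition.

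**Step 2: could unrelated questions be in the coded data?** Yes. Section 13.3.3 centres the coding on the sexuality codebook but allows other behaviours and topics. Section 13.2.3, whose strategy Phase III follows, gives patient question asking as an example of a behaviour to code and allows pain and fatigue discussions to be coded. The exploratory outcome in 13.3.2 needs a count of all questions.

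**Step 3: reproduce the plan's figure.** Inputs from 13.3.4: 64 recordings per arm, 15% versus 38%, two-sided 5%, Fisher's exact test. Power is the sum, over all pairs (i, j) with Fisher p ≤ 0.05, of Bin(i; 64, 0.15) × Bin(j; 64, 0.38). The result is 0.801, against a stated 80%. The same calculation for outcome B (45 per arm, 22% versus 52%) gives 0.803. Neither stated figure is wrong, and restoring the topic to the rule changes neither.

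**Step 4: illustrate the literal rule.** The documents give no rate for questions on any topic. Three assumptions are therefore needed: the 15% and 38% are sexual-health question rates; other questions occur in a share q of visits, equal in both arms; and they are independent of sexual-health questions. The any-question rate is then 1 − (1 − p)(1 − q), with p = 0.15 or 0.38.

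| q | Control | Intervention | Fisher power, 64 per arm |
|---|---|---|---|
| 0 | 15.0% | 38.0% | 80.1% |
| 10% | 1 − 0.85 × 0.90 = 23.5% | 1 − 0.62 × 0.90 = 44.2% | 64% |
| 30% | 1 − 0.85 × 0.70 = 40.5% | 1 − 0.62 × 0.70 = 56.6% | 36% |
| 50% | 1 − 0.85 × 0.50 = 57.5% | 1 − 0.62 × 0.50 = 69.0% | 22% |
| 70% | 1 − 0.85 × 0.30 = 74.5% | 1 − 0.62 × 0.30 = 81.4% | 11% |

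**Step 5: illustrate the opposite error.** Assume sexual-health questions stay at 15% in both arms, while training raises other questions from 30% to 60% of visits. The literal rule then compares 1 − 0.85 × 0.70 = 40.5% with 1 − 0.85 × 0.40 = 66.0%. Fisher's test is significant 78% of the time, although nothing has changed for Hypothesis III.

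**The case against.** The best defence is that the sentence in 13.3.3 is shorthand. It uses the label 2A, which 13.3.1 has already defined with the topic, and its purpose is to set the cut at one question. The codebook is about sexuality, and the same paragraph says these behaviours were rare in Phase II. The drafters shorten elsewhere: 13.3.3 later describes the exploratory count without the word that marks it as all-topic in 13.3.2. A coder holding the sexuality codebook would probably not score a scheduling question.

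As an account of intent, this is probably right. It does not remove the written conflict. Words without a topic also describe the exploratory all-topic measure, and the adjacent 2B sentences do name the topic.

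Two further objections stand in full. First, a reader might infer that the rule codes a different variable from the one the trial was powered on. The document does not establish that, because 13.3.4 describes the powered variable as "the proportion of visits where the patient asks a question", the same unqualified form. It is likely that the 15% is a sexual-health question rate, since 13.3.4 presents it under the primary outcomes, but this is not stated. Section 4.3.3 reports that Phase II patients seldom asked questions at all, which leaves some room for a low any-question rate.

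Second, the power losses rest on an assumed q and on training having no effect on other questions. They are not findings about this trial. The total sample size is also set by the belief outcomes (13.3.4), so 2A does not determine it.

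**Conclusion.** The 2A coding rule is wrong as written: it contradicts the definition of a primary outcome and, applied literally, does not test Hypothesis III. This rests on the text alone and needs no assumption. It should be corrected before the recordings are coded.

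It is also unclear which variable the 15% control rate describes. If it is the Phase II rate of visits with a sexual-health question, the stated power stands at 80.1%. If it is an any-question rate, the power for 2A as defined has not been shown.

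The documents do not support saying that the stated power is wrong, or that the trial will lose a particular amount of power. The range of 64% to 11% for q from 10% to 70% shows only how sensitive the outcome is to the missing words.

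**What to change.** 1. In 13.3.3, in the 2A rule, add after the word questions: *pertaining to sexual health (as defined in the codebook)*.
2. In 13.3.4, make the same change to the description of outcome A.
3. Keep the count of questions on all topics as an exploratory outcome only.
4. In 13.3.4, state what the 15% measured in Phase II. If it was the sexual-health question rate, no figure changes. If it was an any-question rate, restate the power for 2A using the sexual-health rate.

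The cost is one phrase in two places and one sentence on the source of the 15%, with no extra data collection. Only the second branch of item 4 needs a new calculation.

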Skills-Based Training. Details of this intervention have been informed by the results from both Phases I and II. Using a social cognitive framework,⁸² the 20-minute intervention (Starting the Conversation) consists of an informational and skills-based video and accompanying workbook. This intervention is designed to increase self-efficacy and outcome expectancies for communicating with providers about menopausal and sexual health, reduce barriers to communication, and provide basic training in skills for communicating with providers about menopausal and sexual health, including prioritizing concerns, tips for effective communication, communication practice, and self-feedback. Planned communication content and structure are influenced by other skills-based patient-focused training interventions in cancer^{57,83}, results from Phases I and II of our study (e.g., patient cognitive interviews, data from clinic dialogue

suggesting that patients infrequently ask questions during clinic visits), current research on menopausal and sexual side effects of breast cancer treatment, and the input of study team members who have expertise in patient-provider communication ([name]), behavioral patient interventions ([name], [name], [name]), breast cancer ([name]), and menopausal and sexual health for women with cancer ([name], [name]). In addition to viewing the module, participants will be sent a workbook to go along with the video module. Patients in the Skills-Based Training condition will also receive resources on menopausal and sexual health for breast cancer survivors, in the form of a list of informational resources (e.g., websites, Fox Chase resources or clinics). Control Condition. Patients randomized to the Control group will receive the same list of menopausal and sexual health resource guide as the patients in the Skills-Based Training group, but will not be asked to participate in the Starting the Conversation intervention. After completion of all study measures and the recording of their clinic visit, interested Control group patients will be offered the opportunity to participate in Starting the Conversation (i.e., to watch the video and use the workbook).

The patient's first clinic appointment following her participation in the patient training program with the post-training provider will be audio recorded using the methodology described earlier for recording of the provider baseline visits.

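### Primary outcome 2B drops visits in which the provider raises sexual health, a post-randomisation event, and the plan names no all-visit analysis or by-arm count to read beside it

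*Combined protocol and SAP*

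**What the plan says.** Section 13.3.1 lists outcome 2B as "the proportion of clinic visits in which the patient raises the topic of sexual health", with no restriction on which visits count. Hypothesis III in section 2.3 is equally unrestricted: it expects trained patients to be more likely to "raise the topic of sexuality than patients in the Control condition".

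Section 13.3.3 codes a visit yes if the patient raises the topic and no if nobody does. It then adds: "If the provider brings up sexual health, these visits will be excluded from analysis of outcome 2B". The reason given is that "it is impossible to know if the patient may have brought up sexual health if the doctor had not done so". Fisher's exact test is the main analysis.

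Section 13.3.4 allows for the loss: "We also anticipate that 70% of visits will be informative for outcome B", and power is computed "assuming 45 informative visits per arm".

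Section 13.3.3 also promises general summaries of all variables, a mixed logistic model if feasible, optional moderator models and optional checks of model assumptions. None of these brings the excluded visits back, and none calls for their number by arm.

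**The concern.** The recorded visit takes place after randomisation and after the training materials have been delivered (section 4.3.3). Whether the provider raises sexual health is therefore a post-randomisation event. The intervention is meant to "provide basic training in skills for communicating with providers about menopausal and sexual health", so it can plausibly alter who speaks first. A trained patient who speaks early pre-empts her provider, and her visit stays in. A control patient who waits may be pre-empted, and her visit drops out. Randomisation does not protect a comparison of the subsets that remain, and the single 70% informative share assumed for both arms is the quantity that training could change.

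What is at stake is interpretation. The 2B percentages alone cannot separate more patients being ready to raise the topic from a change in speaking order.

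A smaller point concerns wording. The exclusion rule does not say first. Read literally, a visit that the patient opens and the provider then takes up is both a yes and an exclusion. The stated reason, and the clinician-initiated code in section 13.2.2, suggest that first is meant.

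**Working it through.** **Inputs from section 13.3.4:** 64 recordings per arm; 70% informative; 22% (control) against 52% (skills); two-sided 5%. All powers below enumerate Fisher's exact test in full, with expected informative numbers rounded.

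**The plan's own figure.** Informative visits: 0.70 × 64 = 44.8, so 45 per arm. Power for 22% vs 52% is 80.3%. The stated power reproduces.

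**All-visit version at the planned rates.** If provider-raised visits are kept and counted as no, the rates are 0.70 × 22% = 15.4% and 0.70 × 52% = 36.4%. With 64 per arm, power is 72.4%.

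**Scenarios 1 and 2: change in speaking order.** These are assumptions, not document figures. Let r be readiness, the share of patients who would raise the topic if not pre-empted. Providers would raise it in 30% of visits, independently of r. In control, the provider always speaks first when both would. In the skills arm, the patient speaks first in a share f of those overlapping visits. Then:

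- patient-first = 0.7r + 0.3rf
- provider-first = 0.30 − 0.3rf
- 2B = patient-first / (1 − provider-first)

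Worked case, r = 0.22 and f = 1: patient-first = 0.154 + 0.066 = 22.0%; provider-first = 0.30 − 0.066 = 23.4%; 2B = 0.220 / 0.766 = 28.7%.

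Control is fixed at patient-first 15.4%, provider-first 30%, 2B 22% and n = 45.

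| Skills arm r, f | Patient-first | Provider-first | 2B | n | Planned test rejects | All-visit test rejects |
|---|---|---|---|---|---|---|
| 0.22, 0 | 15.4% | 30.0% | 22.0% | 45 | 2.6% | 2.8% |
| 0.22, 0.5 | 18.7% | 26.7% | 25.5% | 47 | 5.1% | 4.9% |
| 0.22, 1 | 22.0% | 23.4% | 28.7% | 49 | 8.6% | 11.1% |
| 0.52, 0 | 36.4% | 30.0% | 52.0% | 45 | 80.3% | 72.4% |
| 0.52, 0.5 | 44.2% | 22.2% | 56.8% | 50 | 93.3% | 93.4% |
| 0.52, 1 | 52.0% | 14.4% | 60.7% | 55 | 97.9% | 99.2% |

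**Sensitivity to the control assumption.** If control patients speak first in half of the overlapping visits and trained patients in all of them, with r = 0.22 in both arms, 2B is 25.5% vs 28.7%. The planned test rejects 5.2% of the time and the all-visit test 4.8%.

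**Scenario 3: change in which visits are dropped, with equal readiness.** Assume that 40% of patients would raise the topic half the time and 60% would do so 8% of the time. In control, providers speak first in 40% and 20% of these groups. Kept: 0.4 × 0.6 + 0.6 × 0.8 = 0.72. Yes: 0.4 × 0.6 × 0.5 + 0.6 × 0.8 × 0.08 = 0.1584. So 2B = 22.0%. If the skills-arm provider-first rate in the more willing group becomes 60% or 20%, 2B is 0.1184 / 0.64 = 18.5% or 0.1984 / 0.80 = 24.8%. Expected numbers are 46 vs 41 or 51. Rejection is 5.1% or 4.5% for the planned test, and 6.2% or 5.8% for all visits. The shift can go either way.

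**Literal reading of the exclusion.** Suppose a quarter or a half of patient-opened visits were dropped in both arms because the provider later took up the topic. Starting from the planned rates, 2B power would fall from 80.3% to about 72% or 60%.

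**Precision of the proposed count.** The 95% interval for the difference in provider-first share, 64 per arm, has half-width 1.96 × √(2 × 0.3 × 0.7 / 64) = 15.9 points at 30% vs 30%, and 14.1 points at 30% vs 14.4%.

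**The case against.** The exclusion is prespecified, reasoned and allowed for in the power statement, and a one-line outcome list is normally completed by the analysis section. All of that is true, but none of it shows whether the arms lose visits differently.

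The all-visit test does not isolate readiness either. Under full pre-emption with equal readiness it rejects more often than the planned test (11.1% vs 8.6%), and it does so in both versions of scenario 3. This stands, and it is why the test is proposed as supporting only. It does, however, compare the groups as randomised and match the outcome as listed. A patient who speaks before her provider has done what Hypothesis III predicts, so a difference in patient-first visits is a real effect on that measure.

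The 8.6% figure also relies on control patients never speaking first in overlapping visits, which no document supports. The sensitivity case brings it down to 5.2%, so it should be read as one end of a range.

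Finally, the excluded count can be recovered by subtracting the 2B table totals from the recordings per arm, and outcome 2A already uses all visits. Subtraction by a reader is not a planned analysis, and 2A measures a different behaviour, asking a question. The word first is a clarification, since the intended meaning is fairly clear.

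**Conclusion.** The concern holds as a cheap improvement. Outcome 2B conditions on a post-randomisation event that the training can change, and the plan commits to nothing that would let a reader judge the consequence. The effect is likely modest. With equal readiness, the assumed scenarios move 2B by about 3 to 7 points from 22%, and the planned test rejects 4.5% to 8.6% of the time. At the planned effect, pre-emption raises 2B from 52% to between 56.8% and 60.7%. These sizes rest on the assumed 30% provider share and the assumed speaking-order rules; the documents give no by-arm figures. The stated 2B power, outcome 2A and the belief outcomes are not in question.

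**What to change.** Keep the planned conditional Fisher test of 2B and add to section 13.3.3:

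> As a supporting analysis, all recorded visits will be compared by randomised arm with Fisher's exact test (patient raises sexual health first = yes; otherwise no). Counts of patient-first, provider-first and not-raised visits will be given by arm, with the difference in provider-first proportion and its 95% CI. Outcome 2B will be interpreted together with these results.

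Reword the exclusion so that it applies only when the provider brings up sexual health first, and use the same wording in section 13.3.4.

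Do not require the provider-first shares to be similar. Successful pre-emption itself lowers that share, and with equal true rates of 30% a gap of 10 points or more arises by chance about 21% of the time.

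The cost is a few sentences and one small table. The 2B rule already needs a code for who raised the topic, and Phase III coding proceeds "using a similar strategy as described for the Provider Training Study (Phase II"), which includes clinician-initiated discussion. The drawbacks are that the all-visit version has about 72% power at the planned rates and counts a pre-empted patient as a no, so it answers a somewhat different question. The planned test and its power do not change.
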